1.0 Objectives

1.1 Study Objectives

The purpose of the study is to determine if the dose of contrast administered for computed tomographic arteriograms (CTA) can be reduced without degradation of image quality. The hypothesis is that there is no difference in image quality using ultra-low dose contrast in CTA exams compared to routine dose exams.

1.2 Primary Study Endpoints

The objective is to prospectively evaluate image quality of CTA examinations performed with an ultralow contrast dose protocol. The primary endpoint would be to show that there is no statistical difference in the quality of the images.

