7.0 Study Design and Procedures

7.1 Study Design

Any adult patient scheduled for routine CTA meeting the inclusion/exclusion criteria and providing consent will be included in the study. The patient will be administered a low dose of intravenous contrast based on the study examination as described below. The contrast agent being used is Omnipaque. The scan will be performed under the supervision of the primary investigator or the described team members to make sure that the study is of diagnostic quality.

The following dose protocols will be followed:

CTA of the chest: 40 mL of intravenous contrast at a rate of 5mL/sec. A region of interest (ROI) to trigger the scan will be placed in the aortic arch. If scan is performed using high pitch helical mode, the scan delay will be increased by 2 seconds.

CTA of the abdomen OR or CTA of the chest and abdomen or CTA of the abdomen and pelvis or CTA of the chest, abdomen and pelvis: 50 mL of intravenous contrast at a rate 5mL/sec. A region of interest (ROI) to trigger the scan will be placed in the aortic arch. If scan is performed using high pitch helical mode, the scan delay will be increased by 2 seconds.

All other imaging parameters will remain unchanged, given that the subjects enrolled will be clinical patients of the principle investigator.

Following the examination, the primary investigator (PI) or team members will evaluate the images obtained with low contrast dose and each patient's prior CTA examination performed with routine contrast dose. This will be done by quantitative and qualitative measures. For the quantitative portion, the PI or team members will place regions of interest on predetermined arterial locations to obtain measure the degree of opacification. For qualitative measurement, the images will be presented in a blind fashion to two thoracic trained board certified radiologists and a board certified interventional radiologist to determine the quality of the images based on a Likert numerical scale. Qualitative and quantitative data for the images obtained with low contrast dose and those for the prior CTA examinations performed with routine contrast dose will be compared. This data along with details of the

scan protocol (dose, dose rate, scanning parameters etc.) and demographic data (such as sex, age and BMI at the time of examination) will be recorded in Redcap.

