8.0 Subject Numbers and Statistical Plan

8.1 Number of Subjects

The number of study subjects anticipated is 180 patients.

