8.2 Sample size determination

This number of patients achieves 80% power, with a 7.5% equivalence margin, at a 5% significance level using a two-sided equivalence test of correlated proportions when the actual difference of the proportions is zero.

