8.3 Statistical methods

Measured data from CTAs performed with low intravenous contrast dose and from CTAs performed with routine intravenous contrast dose for each patient will be analyzed using paired t-tests. The statistical methodology will be reviewed by consultation with biostatistics.

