10.0 Data and Safety Monitoring Plan

10.1 Periodic evaluation of data

The PI and research study team will periodically evaluate the data and communicate regarding subject safety. Data collected for the first 20 patients will be summarized and submitted to the IRB for review to

ensure safety of subjects. This data will include information about image quality of the CTA examinations, any adverse events that occurred, and how many subjects required repeat scans.

- **10.2** Data that are reviewed Data acquired during low-contrast CTA will be reviewed.
- **10.3** Method of collection of safety information Data will be collected at time of screening and CTA
- **10.4** Frequency of data collection Data will be collected at time of screening and CTA
- **10.5** Individuals reviewing the data The PI and research study team will be responsible for reviewing data.
- **10.6** Frequency of review of cumulative data Cumulative data will be reviewed on a weekly basis by the principal investigator and study team members.
- **10.7** Statistical tests Statistical tests are as outlined in section 8.2 and 8.3.
- **10.8** Suspension of research Not Applicable

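### Success is defined as no statistical difference and analysed by paired t-tests, while the 7.5% equivalence test that sized the trial never reaches the endpoint or the methods

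*Combined protocol and SAP*

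**What the plan says.** - **Objective and hypothesis (Section 1.1).** The study asks whether contrast dose "can be reduced without degradation of image quality". The hypothesis is one of no difference, with no margin.
- **Primary endpoint (Section 1.2).** "The primary endpoint would be to show that there is no statistical difference in the quality of the images". There is again no margin, and Section 1.3 lists no secondary endpoints.
- **Data (Section 7.1).** Opacification is measured in regions of interest. Three radiologists read the images blind "to determine the quality of the images based on a Likert numerical scale". No cut-point or reader-combination rule turns either measure into a proportion.
- **Sample size (Sections 8.1 and 8.2).** 180 patients are planned for 80% power with a 7.5% margin at a 5% level, "using a two-sided equivalence test of correlated proportions when the actual difference of the proportions is zero".
- **Methods (Section 8.3).** Measured data from the two scans "for each patient will be analyzed using paired t-tests". The section adds that biostatistics will be consulted.
- **Monitoring plan (Section 10.7).** "Statistical tests are as outlined in section 8.2 and 8.3". It does not say which test decides the trial.

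**The concern.** A paired t-test asks whether the data contradict a zero difference. When they do not, the cause may be that the scans are equally good, or that the estimate is too imprecise to tell. Only a bound on the loss separates these, and Section 1.1 needs such a bound because it asks about degradation. The plan has one, the 7.5% margin, but it appears only in the sample-size paragraph.

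Two consequences follow. The rule written into the endpoint is not the one the trial was powered for. And the powered test cannot yet be run, because it needs a yes/no outcome per scan and the plan collects Likert scores and opacification values. At stake is the trial's only endpoint: a claim of preserved quality could be published with no limit on the loss still compatible with the data.

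**Working it through.** **Inputs from the plan.** N = 180 pairs, margin m = 0.075, power 80%, significance level 5%, true difference 0.

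**Inputs assumed.** The outcome is binary (adequate or inadequate). The discordant proportion ψ (pairs adequate on one scan only) is not stated in the plan. Since 8.2 does not say how the 5% is split, both 5% and 2.5% per side are carried.

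**Step 1: reproduce 180.** By normal approximation, n = ψ(z₁₋ₐ + z₀.₉₀)² / m², so ψ = 180 × 0.075² / (z₁₋ₐ + 1.282)².
- 5% per side: 1.0125 / (1.645 + 1.282)² gives ψ ≈ 0.118.
- 2.5% per side: 1.0125 / (1.960 + 1.282)² gives ψ ≈ 0.096.

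So 180 is attainable, but only with an unstated ψ. At 5% per side, ψ = 0.05 would need 77 pairs, 0.10 would need 153, 0.15 would need 229 and 0.20 would need 305.

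**Step 2: one data set, two rules.** Take 7 patients adequate only on low dose and 14 only on routine dose.
- Difference = (7 − 14)/180 = −3.9 points.
- SE = √[(21/180 − 0.0389²)/179] = 0.0254; t = −1.53; p = 0.127. Section 1.2 would call this no difference.
- The 90% paired score interval is −8.4 to +0.3 points. It crosses −7.5, so equivalence is not shown.

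The reverse can also occur. With 0 and 5 discordant pairs the difference is −2.8 points with t-test p = 0.025, yet the 90% score interval of −5.6 to −1.3 lies inside the margin.

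**Step 3: operating characteristics at n = 180.** Exact enumeration over the discordant counts. The t-test is two-sided at 5%; equivalence uses the per-side level that goes with each ψ. Each cell gives ψ = 0.118 (5% per side) / ψ = 0.096 (2.5% per side).

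| True loss | t-test non-significant | Equivalence shown, Wald | Equivalence shown, score | t-test non-significant and score equivalence not shown |
|---|---|---|---|---|
| 0 | 95% / 95% | 79% / 78% | 75% / 70% | 19% / 25% |
| 5 points | 48% / 40% | 27% / 23% | 23% / 15% | 25% / 25% |
| 7.5 points | 12% / 5% | 6% / 5% | 5% / 2% | 8% / 4% |

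**Step 4: precision.** The non-significance rule rewards small samples. By simulation with ψ = 0.118 and a true loss at the margin, it passes 91.7% of the time at n = 20, 44.8% at n = 90, 12.3% at n = 180 and 0.7% at n = 360. Equivalence by Wald at 5% per side stays between about 5% and 8% over that range.

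**Sensitivity outside the implied design.** At ψ = 0.20 and n = 180 the t-test rule passes a 7.5-point loss 37% of the time. Equivalence power would then be only about 45%, so the sizing in 8.2 would fail too.

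**The case against.** The best defence is that the plan already contains the right test. Section 10.7 cites 8.2 as well as 8.3 as a source of tests, and the measured data in 8.3 may mean only the opacification values, leaving the equivalence test for image quality. That reading is possible, but no passage states it. Section 10.7 belongs to the monitoring plan and does not rank the two tests, and Section 1.2 states a different criterion. Even on this reading the equivalence test has no defined outcome. The promised biostatistics consultation shows the section was provisional; it does not supply a rule.

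Three objections to the numbers have force:
- The plan proposes no t-test on a dichotomised outcome, and the 7.5-point margin has no counterpart on Hounsfield units or Likert scores. The rates above are illustrations, not the error rates of 8.3 as written.
- At the margin the excess over equivalence testing is modest or nil at the implied discordance. A 5-point loss lies inside the margin, so passing there is not an error by the standard of 8.2.
- The 0-versus-5 example is remote. Significant t-test with score equivalence shown has probability 0.03% to 0.25% under the implied design, and exact McNemar gives p = 0.0625 for those counts. The 7-versus-14 example carries the point alone.

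None of this supplies the missing link between 1.2, 8.2 and 8.3.

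**Conclusion.** The concern holds and must be fixed before the data are analysed. That part rests on the text alone: the endpoint and methods use a difference test, the sizing uses an equivalence test, and the equivalence test lacks a defined proportion.

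The size is conditional on a binary outcome and on the discordance inferred from 8.2. There, roughly one trial in five to one in four with no true difference, and one in four with a 5-point loss, would announce no difference without having shown equivalence. The main harm is an unsupported claim rather than a large rise in false passes at the margin, which go from 5% to 12% (score equivalence versus t-test rule) at 11.8% discordance and from 2% to 5% at 9.6%.

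**What to change.** Amend Sections 1.2, 8.2 and 8.3 before the data are seen.

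1. **Outcome.** Name the primary image-quality measure, set the Likert cut-point for adequate quality, and state how the three readers' scores combine into one result per scan.
2. **Decision rule.** Declare success only if the 90% interval for the paired difference in proportions (low minus routine) lies within ±7.5 points, that is, two one-sided 5% tests. A paired score interval is preferable to Wald: at the margin with 11.8% discordance the error is 4.6% against 6.4%. Since Section 1.1 asks about degradation, one-sided non-inferiority with the same margin is an alternative.
3. **Sizing.** State the per-side level, the assumed discordance and the test method in 8.2.
4. **t-tests.** Keep them for Hounsfield units and Likert scores as descriptive results with confidence intervals, and say that non-significance will not be read as equivalence.

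**Cost.** Protocol text only, with no new readers or data. If 180 is kept, score equivalence at 5% per side has 75% power at 11.8% discordance (Wald 79%) and reaches 80% if discordance is 10.7% or lower. Holding 80% at 11.8% takes about 194 pairs. Score non-inferiority with 180 has 88% power at one-sided 5%, or 79% at one-sided 2.5%. The per-side level matters: score equivalence at 2.5% per side and 11.8% discordance has only 58% power, so that choice would call for more patients.

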1.3 Secondary Study Endpoints

Not Applicable

2.0 Background

2.1 Scientific Background and Gaps

Currently, at our institution, routine CTA examinations are obtained with a dose of 100mL of intravenous contrast. In the setting of renal dysfunction, this dose is reduced to 75mL to minimize the risk of contrast induced nephropathy. This dose can be further adjusted giving some flexibility depending on the BMI of the patient and type of scanner used. Given the recent advancements of computed tomography hardware, the scanning speed has greatly increased allowing for reduction in contrast dose. However, at our institution, the dosage and administration rate of intravenous contrast has not yet been adjusted to take advantage of improvements in scanning hardware.

2.2 Previous Data

A small number of patients have been imaged with a decreased contrast dose (up to 60% less contrast volume). By taking advantage of scanner speed and number of detectors, a smaller overall dose can be given while still obtaining adequate diagnostic imaging. Quantitative measurements of vascular enhancement (in Hounsfield units) at select locations show no differences in vascular opacification. In addition, qualitative evaluation of these images by board certified diagnostic radiologists show no difference in image quality between examinations performed with reduced contrast dose versus examinations performed with standard contrast dose. This data suggests that the same quality of images can be obtained with a lower dose of contrast minimizing the risk of contrast induced nephropathy. No references are available at this time regarding the rate of re-imaging due to non-interpretable CTA studies. In correspondence with several CT technologists, they stated that in their experience, rarely does a CTA of the chest or chest, abdomen and pelvis have to be repeated

2.3 Study Rationale

CTA is the imaging of choice for the evaluation of the aorta. Aortic CTAs are performed for evaluation of acute aortic syndromes, vasculitidies, as well as chronic conditions such as aortic aneurysms and congenital anomalies. Examinations are performed for pre-operative evaluation and post-operative follow up in many of these patients. This patient population includes patients with many comorbidities, such as hypertension and diabetes, as well as elderly patients. All these conditions contribute to renal dysfunction. For this reason, the radiology department at this institution has a policy to evaluate renal function before a contrast enhanced CT scan in the setting of increased age (>60 years), history of renal dysfunction or diabetes. Decreasing the contrast dose is important to prevent further damage to the kidneys by contrast induced nephropathy (CIN). It is thought that reducing the contrast dose will reduce

the risk of nephropathy. Development of a low dose protocol would potentially decrease the risk of contrast induced nephropathy in this patient population.

3.0 Inclusion and Exclusion Criteria

3.1 Inclusion Criteria

- 1. Any adult patient scheduled for a computed tomographic arteriogram (CTA) of the chest or CTA of the abdomen or CTA of the chest and abdomen or CTA of the abdomen and pelvis or CTA of the chest, abdomen and pelvis who had undergone a prior CTA of the same region performed with the standard contrast dose (100 mL) at this institution will be included in the study.
- 2. The follow-up scan will be routine standard of care, no emergency imaging patient will be approached for this research.

3.2 Exclusion Criteria

- 1. Patients with no prior CTA imaging for comparison.
- 2. Any pediatric patient (age <18).
- 3. BMI >40
- 4. Inability to follow instructions.
- 5. Allergy to intravenous contrast.
- 6. GFR less than 60 mL/min/1.73 m²⁻GFR should be within normal range. This would allow a repeat study if needed and not pose an increased risk to renal dysfunction.
- 7. Cognitively Impaired Adults
- 8. non-English speaking patients
- 9. Pregnant Females
- 10. Endoleak studies decreased contrast makes evaluation of an endoleak difficult on delayed imaging.

3.3 Early Withdrawal of Subjects

3.3.1 Criteria for removal from study

Patient may decline or withdraw from participation at any time after the consent is signed.

3.3.2 Follow-up for withdrawn subjects

The information required for the study is obtained at the initial time of evaluation. If a person declines to participate, no data will be acquired. There is no reason to follow up withdrawn subjects.

4.0 Recruitment Methods

4.1 Identification of subjects

Medical records of adult patients scheduled for a routine computed tomography arteriogram will be evaluated prior to CTA imaging to identify subjects meeting the inclusion/exclusion criteria.

4.2 Recruitment process

Patients scheduled for routine CTA examinations will be screened, via medical records, to find out if they have had a prior CTA of the aorta with routine dose of intravenous contrast within the past two years. Those patients within this group that meet inclusion criteria and do not have any exclusion criteria will be offered to participate in the study.

4.3 Recruitment materials

Not Applicable

4.4 Eligibility/screening of subjects

We will be entering medical records to screen for eligibility. Therefore, we are requesting a waiver of consent and a HIPAA waiver of authorization to screen for eligibility criteria prior to the consent form being signed.

5.0 Consent Process and Documentation

5.1 Consent Process

5.1.1 Obtaining Informed Consent

5.1.1.1 Timing and Location of Consent

Informed consent will be obtained prior to examination in the IV preparation room or scanner room.

5.1.1.2 Coercion or Undue Influence during Consent

The individual obtaining consent will explain to the patient that participation is voluntary; that they do not have to take part in this research and that they can withdraw at any time. The decision whether or not to participate will have no impact on the availability of their current and future care within PSHMC. They will also be told that there is no compensation or reward for participating in the study.

5.1.2 Waiver or alteration of the informed consent requirement

We will be requesting a waiver to enter medical records to screen for eligibility.

5.2 Consent Documentation

5.2.1 Written Documentation of Consent

Informed consent will be documented through the use of the long form consent. The language used in the informed consent document will be understandable to the subject. Both the subject and the person obtaining consent will sign the document, along with the date informed consent was obtained/given. A copy of the signed and dated informed consent document will be given to the subject. A signed copy of the consent will also be included in the patient's medical record.

5.2.2 Waiver of Documentation of Consent (Implied consent, Verbal consent, etc.) Not Applicable

5.3 Consent – Other Considerations

5.3.1 Non-English Speaking Subjects Not Applicable

5.3.2 Cognitively Impaired Adults

5.3.2.1 Capability of Providing Consent Not Applicable

- 5.3.2.2 Adults Unable To Consent Not Applicable
- 5.3.2.3 Assent of Adults Unable to Consent Not Applicable

Page 5 of 14 (v.08/18/2015)

5.3.3 Subjects who are not yet adults (infants, children, teenagers)

5.3.3.1 Parental Permission

Not Applicable

5.3.3.2 Assent of subjects who are not yet adults Not Applicable

6.0 HIPAA Research Authorization and/or Waiver or Alteration of Authorization

6.1 Authorization and/or Waiver or Alteration of Authorization for the Uses and Disclosures of PHI

Check all that apply:

Not applicable, no identifiable protected health information (PHI) is accessed, used or
disclosed in this study. [Mark all parts of sections 6.2 and 6.3 as not applicable]

- Authorization will be obtained and documented as part of the consent process. [If this is the only box checked, mark sections 6.2 and 6.3 as not applicable]
- Partial waiver is requested for recruitment purposes only (Check this box if patients' medical records will be accessed to determine eligibility before consent/authorization has been obtained). [Complete all parts of sections 6.2 and 6.3]
- **Full waiver is requested for entire research study (e.g., medical record review studies).** [Complete all parts of sections 6.2 and 6.3]
- Alteration is requested to waive requirement for written documentation of authorization (verbal authorization will be obtained). [Complete all parts of sections 6.2 and 6.3]
- 6.2 Waiver or Alteration of Authorization for the Uses and Disclosures of PHI
 - 6.2.1 Access, use or disclosure of PHI representing no more than a minimal risk to the privacy of the individual
 - **6.2.1.1 Plan to protect PHI from improper use or disclosure** Information is included in the "Confidentiality, Privacy and Data Management" section of this protocol.
 - **6.2.1.2 Plan to destroy identifiers or a justification for retaining identifiers** As the CTA scan is part of the patient's medical care, the images, with identifiers, will remain in the patient's medical record. The study linking list will be destroyed as per study guidelines.
 - 6.2.2 Explanation for why the research could not practicably be conducted without access to and use of PHI

Given that subject eligibility is based on previous CTA imaging with standard contrast dose (100 mL), it would not be possible to identify potential subjects without access to their medical records.

6.2.3 Explanation for why the research could not practicably be conducted without the waiver or alteration of authorization

Potential subjects' history of procedures completed at this institution are kept within medical records, which contain PHI. Therefore, without a partial waiver, study team members will not be able to appropriately identify potential subjects.

6.3 Waiver or alteration of authorization statements of agreement

Protected health information obtained as part of this research will not be reused or disclosed to any other person or entity, except as required by law, for authorized oversight of the research study, or for other permitted uses and disclosures according to federal regulations.

The research team will collect only information essential to the study and in accord with the 'Minimum Necessary' standard (information reasonably necessary to accomplish the objectives of the research) per federal regulations.

Access to the information will be limited, to the greatest extent possible, within the research team. All disclosures or releases of identifiable information granted under this waiver will be accounted for and documented.

